8.6 DATA MANAGEMENT

Participant answers to the online survey will be collected using Conformat Horizons software and the data exported via SPSS (.sav) and analyzed using Q-Research Software. The data is stored in the EEA in London, England. The data is isolated on the server. The Conformat Horizons SaaS (software as a service) hosting environments are not “cloud” based. Horizons SaaS hosting environments store the data physically in a specific datacenter, and the management of the datacenter is hosted by Rackspace. Rackspace holds the following security certifications, including ISO27001, Payment Card Industry (PCI DSS), ISO 9001, and is SOC II audited in accordance with SSAE16 / ISAE3402. In order to comply with General Data Protection Regulation (GDPR) only a minimum amount of personal data will be collected in order to fulfill the purposes of the survey. This data will be retained only for as long as the duration of the project. On Conformat Horizons SaaS there is a ‘countdown’ feature whereby the project owner defines a retention period for the whole survey database. The data will be deleted from the Conformat Horizons SaaS environment at that date. Prior to the deletion date, the system will send an e-mail reminding the project owner that the data will be deleted. Data rendered anonymous can be kept indefinitely and will be deleted upon instruction from the project owner.

8.7 DATA ANALYSIS

The analysis will be cross-sectional and descriptive. Categorical data will be summarized by counts and percentages. Continuous data will be summarized using number, median, minimum and maximum values. Missing data will be noted for each variable.

A **positive outcome** reported across key pre-defined questions for each of these objectives would support the effectiveness of the educational material. For this assessment, a positive outcome is defined as at >70% of the survey participants providing a ‘correct’ response (specific questions and responses are outlined in Tables [Table 8](#) and [Table 9](#)). The 70% cut point is based on previous experience from other surveys evaluating the effectiveness of educational materials.

Table 8 - Questions to assess effectiveness in HCP survey

Category of assessment	Question text [Answer options]	Criteria for 'effective assessment'
To assess if materials are being received and read	A2. Which of the following material have you received or had access to? Select all that apply 1. Summary of Product Characteristics (SMPC) 2. Fabrazyme Home Infusion Therapy: A guide for Healthcare professionals treating patients with Fabry disease 3. Fabrazyme Home Infusion Therapy: Manual for Patients with Fabry disease who receive home infusion of Fabrazyme 4. None of the above	Majority of HCPs selecting Code 2
	A3. Have you read the Fabrazyme (agalsidase beta) home infusion educational materials? 1. Yes 2. No	Majority of HCPs selecting Code 1
To assess evaluation of home infusion	B1. Do you use the educational materials to evaluate and select patients for home infusions? 1. Yes 2. No	Majority of HCPs selecting Code 1
	B2. Which of the following criteria must be fulfilled before a patient is deemed eligible for Fabrazyme (agalsidase beta) home infusion? Select all that apply 1. Patient must be medically stable 2. A comprehensive evaluation must be completed before deciding on transfer of therapy to home infusion 3. Patient must have received Fabrazyme infusions for several months in a controlled setting and previous infusions well tolerated 4. Don't know	Majority of HCPs selecting codes 1, 2 and 3
To assess level of training to patients/caregivers	B4. Do you use the Fabrazyme (agalsidase beta) home infusion educational materials when training the patient/caregiver on the home infusion process? 1. Yes 2. No	Majority of HCPs selecting Code 1
	B5. How frequently do you cover each of the following areas when training the patient/caregiver on Fabrazyme home infusion? [1. Always / 2. Regularly / 3. Rarely / 4. Never] a. Importance of adhering to the pre-defined infusion schedule (dose and infusion rate) b. Method of preparation, reconstitution and administration c. Instructions for handling Adverse Events (AEs) and Infusion Associated Reactions (IARs) d. Completing the logbook	Majority of HCPs selecting codes 1 & 2 for each area
To assess knowledge on actions taken in case of IAR and AE	B6. In the event of an infusion associated reaction (IAR) what are the appropriate steps that should be taken? Select all that apply 1. Infusion is immediately discontinued	Majority of HCPs selecting codes 1 & 3

	
2. Infusion is completed and IAR recorded in the logbook
 
3. Patient/Infusion nurse to call the treating physician immediately
 
4. Don't Know
	
To assess implementation of logbook	
C1. How often do you clearly state the Fabrazyme (agalsidase beta) home infusion administration details in the logbook of your Fabry patients? [1. Always / 2. Regularly / 3. Rarely / 4. Never]
	Majority of HCPs selecting codes 1 & 2
	
C2. How often do you review your patients' logbooks? [1. Always / 2. Regularly / 3. Rarely / 4. Never]
	Majority of HCPs selecting codes 1 & 2
	
C4. Considering the logbook, how often do you do each of the following: [1. Always / 2. Regularly / 3. Rarely / 4. Never]
 
a. Document changes to the infusion schedule
 
b. Check the infusion rate
 
c. Check the dose administered
 
d. Discuss logbook with patient/caregiver
	Majority of HCPs selecting codes 1 & 2 for each element

Table 9 - Questions to assess effectiveness in patients/caregivers survey

Category of assessment	Question text [Answer options]	Criteria for 'effective assessment'
To assess if materials are being received read and referred to	
A2. Have you [or the person you care for] received any of the following? Select all that apply
 
1. Package leaflet for Fabrazyme
 
2. Fabrazyme Home Infusion Therapy: Manual for Patients with Fabry disease who receive home infusion of Fabrazyme
 
3. None of the above
	Majority of patients selecting Code 2
	
A3. Have you read the Fabrazyme (agalsidase beta) home infusion educational materials?
 
1. Yes
 
2. No
	Majority of patients selecting Code 1
	
A5. How often do you [or the patient] refer to the educational materials when the home infusions are being done?
 
1. At every infusion
 
2. Frequently
 
3. Rarely
 
4. Never
	Majority of patients selecting Code 1 or 2
To assess knowledge on preparation of infusion	
B3. Which of the following statements are true in relation to the preparation, administration and storage of Fabrazyme. Select all that apply
 
1. The vials must be removed from the refrigerator approximately 30 mins before preparation
 
2. The reconstituted mixture should be shaken up
 
3. The reconstituted solution must be clear and colourless before use
	Majority of patients selecting Code 1, 3 & 4

	
4. The tourniquet should be applied to identify a vein
 
5. The product can be stored at room temperature for 48 hours before use
 
6. None of the above are true
 
7. N/A I don't prepare the infusion on my own
	
To assess knowledge on actions taken in case of AE	
C5. What would you do if [you / the patient] developed a headache and a fever during the infusion?
 
1. Complete the infusion and then rest
 
2. Immediately stop the infusion
 
3. Contact the physician
 
4. Record details in the logbook
 
5. Don't Know
	Majority of patients selecting Code 2, 3 and 4
To assess implementation of logbook	
C1. Considering the Fabrazyme (agalsidase beta) home infusion, how often do you or the nurse who helps you with the infusion (if applicable) do the following actions?
 
[1. Always / 2. Regularly / 3. Rarely / 4. Never]
 
a. Fill out the infusion data in the logbook
 
b. Take the logbook to each appointment with the prescribing physician
	Majority of patients selecting codes 1 & 2 for both actions
	
C2. How often do you or the nurse who helps you with the infusion report changes about the infusion (dose or infusion rate) in [your / the patient's] logbook?
 
1. Always
 
2. Regularly
 
3. Rarely
 
4. Never
 
5. N/A There have been no changes
	Majority of patients selecting codes 1 or 2 (excluding those selecting code 5 from calculation)
	
C6. If [you / the patient] had a side effect, should you report the side effect in your log book?
 
1. Yes, always
 
2. Only if I think it's serious
 
3. No, it is not necessary
	Majority of patients selecting codes 1
	
C7. How often do you review the logbook with [your / the patient's] physician?
 
1. Always
 
2. Regularly
 
3. Rarely
 
4. Never
	Majority of patients selecting codes 1 or 2

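### Section 8.7 sets a positive outcome at more than 70% correct, but all 19 criterion cells in Tables 8 and 9 ask only for an undefined majority

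*Protocol*

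**What the plan says.** Protocol section 8.7 describes the analysis as descriptive and then sets one numerical rule: "a positive outcome is defined as at >70% of the survey participants providing a" correct response. It points to Tables 8 and 9 for the questions and responses concerned, and gives a basis for the figure: "The 70% cut point is based on previous experience from other surveys evaluating the effectiveness of educational materials".

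Both tables have a column headed "Criteria for 'effective assessment". Each cell in it names a quantity and the qualifying answer codes, and the quantity is always a majority:

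- Table 8 (HCPs), 10 rows: A2, A3, B1, B2, B4, B5, B6, C1, C2, C4. Examples are "Majority of HCPs selecting Code 2" for A2 and "Majority of HCPs selecting codes 1 & 3" for B6.
- Table 9 (patients/caregivers), 9 rows: A2, A3, A5, B3, C5, C1, C2, C6, C7. Examples are "Majority of patients selecting Code 2" for A2, "Majority of patients selecting Code 2, 3 and 4" for C5 and "Majority of patients selecting codes 1 or 2" for C7.

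No cell gives a percentage, and the protocol nowhere says what a majority means.

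**The concern.** The text and the tables describe success for the same questions in different terms. In ordinary use a majority is anything above 50%, well short of more than 70%. The column heading presents the cells as the criteria, and each cell can be applied by itself as a complete pass rule. For patient item C2 the cell even fixes the denominator, by leaving out those who answer code 5. Someone programming the analysis from the tables would have no prompt to apply 70%.

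The 70% figure is the only stated rule that turns the percentages into a statement about effectiveness. If its wording stays open, the choice between the two bars could be made after the results are known.

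**Working it through.** **Inputs.** Target sizes are 34 HCPs (section 8.5.1) and 18 patients/caregivers (section 8.5.2). The text threshold is more than 70% (section 8.7). The table threshold is a majority, taken here as more than 50%; that meaning is an assumption, since the protocol gives none.

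**The plan's own figures.** Tables 6 and 7 state no confidence level. A two-sided 95% Wald half-width, 1.96 × √(p(1−p)/n), reproduces them:

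- n=34: 13.4, 15.4 and 16.5 points at 80, 70 and 60%.
- n=18: 18.5, 20.0, 21.2 and 22.6 points at 80, 75, 70 and 60%.

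The planning levels therefore include 60% and 70%, so results in the disputed band are ones the protocol itself contemplates.

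**Counts needed.**

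- n=34: half is 17, so a majority needs at least 18 (52.9%). 0.7 × 34 = 23.8, so more than 70% needs at least 24 (70.6%). The rules conflict at 18 to 23 correct (52.9% to 67.6%).
- n=18: half is 9, so a majority needs at least 10 (55.6%). 0.7 × 18 = 12.6, so more than 70% needs at least 13 (72.2%). The rules conflict at 10 to 12 correct (55.6% to 66.7%).

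**Chance of conflict on one question.** Let X be binomial(n, p), with p the true correct rate and respondents independent. The rules disagree with probability P(18 ≤ X ≤ 23) at n=34 and P(10 ≤ X ≤ 12) at n=18.

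| n | p | P(passes majority) | P(passes >70%) | P(rules disagree) |
|---|---|---|---|---|
| 34 | 0.60 | 0.845 | 0.138 | 0.71 |
| 34 | 0.65 | 0.949 | 0.313 | 0.64 |
| 34 | 0.70 | 0.989 | 0.554 | 0.43 |
| 34 | 0.80 | 1.000 | 0.938 | 0.06 |
| 18 | 0.60 | 0.737 | 0.209 | 0.53 |
| 18 | 0.65 | 0.861 | 0.355 | 0.51 |
| 18 | 0.70 | 0.940 | 0.534 | 0.41 |
| 18 | 0.80 | 0.996 | 0.867 | 0.13 |

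**The phrase before the 70% sign.** The sentence in section 8.7 reads as a blend of at least 70% and more than 70%. Neither 23.8 nor 12.6 is a whole number, so the two readings agree at n=34 and n=18. They differ where 70% is a whole count, for example 14 of 20 or 21 of 30. Patient item C2 could also reach such a denominator once code 5 is removed: with 10 respondents left, 7 of 10 is exactly 70%.

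**The case against.** The strongest reply is that the protocol already settles the matter. A positive outcome is defined once, at 70%, with a stated basis and in the singular. The same sentence cites the tables for questions and responses, so their job would be to show which codes count as correct. No passage names 50% as a threshold, and the precision tables cover 60 to 80% and leave 50% out. This stands as far as intent goes: 70% is the better-supported reading. It does not remove the inconsistency, because the column is headed as criteria and every cell carries its own undefined quantity.

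A reader might infer more: that one result can be both positive and negative under the protocol, or that the wording decides the regulatory conclusion. The documents do not support either. The tables never use the term positive outcome, so a 60% result is not one under any sentence of the protocol. Section 8.7 says positive outcomes would support effectiveness, with no hypothesis test attached, and section 11.2 asks for the results to be read together with safety and clinical outcomes. Counts and percentages will be reported, so a reader can apply either bar afterwards.

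The size of the problem also depends on the true rate. It is large at 60 to 70% and small at 80%, so quoting 60% alone would mislead.

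**Conclusion.** The inconsistency is real, and it sits in the study's only decision threshold. The text supports more than 70%, while all 19 table cells state a looser, undefined criterion under a heading that invites their use. At the target sizes the two differ for 18 to 23 of 34 HCPs and 10 to 12 of 18 patients. Items at or below 50%, or above 70%, are judged the same way under both.

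This rests on the ordinary meaning of majority and, for the probabilities, on independent respondents at the full target sizes. A statistical analysis plan might clarify the point, but the conflict lies within the protocol's own text and should be removed there. It is a wording defect that is cheap to cure; no data or design feature is affected.

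**What to change.** In every criterion cell of Tables 8 and 9, replace the words for a majority of HCPs or patients with more than 70% of them. Express this as a percentage of the respondents counted for that item; for patient item C2, that is after code 5 is excluded. Keep fixed counts out of the cells: C2 has a variable denominator, and section 8.9 warns that the intended sample may not be reached.

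In section 8.7, correct the garbled phrase to read more than 70%, and add a sentence stating that this is the only threshold used.

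The cost is an edit to two tables and two sentences. The downside is that items above 50% and up to 70% cannot be called effective.

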6 RATIONALE AND BACKGROUND

6.1 BACKGROUND

Fabrazyme (agalsidase beta) indication and administration

Fabrazyme contains recombinant human α -galactosidase A (r-h α GAL) as the active ingredient. Fabrazyme is indicated for long-term enzyme replacement therapy in patients with a confirmed diagnosis of Fabry disease. Fabrazyme should be supervised by a physician experienced in the management of patients with Fabry Disease or other inherited metabolic diseases. The recommended dose of Fabrazyme is 1 mg/kg body weight administered once every 2 weeks as an intravenous infusion.

Infusion of Fabrazyme at home may be considered for patients who are tolerating their infusions well. The decision to have a patient move to home infusion should be made after evaluation and recommendation by the treating physician.

Additional Risk Minimization

As part of the Fabrazyme risk management plan (RMP, version 1.2, 19 September 2011), additional risk minimization activities are included to educate patients and HCPs on key elements of Fabrazyme infusion in the home setting.

Educational materials have been developed and approved by European Medicines Agency (EMA) as additional risk minimization activities for Fabrazyme home infusion therapy, and serve as educational resources for both treating HCP and patients.

The Fabrazyme educational pack contains the following:

- A) Home infusion manual for HCPs
- B) Home infusion manual for patients
- C) Summary of Product Characteristics or Package Leaflet

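### Five scored items ask about the educational materials collectively, so a respondent who knows only the SmPC or package leaflet could be counted as having read or used the manual

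*Protocol*

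**What the plan says.** Section 6.1 of the protocol introduces the pack with "The Fabrazyme educational pack contains the following" and lists three components: a manual for HCPs, a manual for patients, and "Summary of Product Characteristics or Package Leaflet". Just before that list it describes the materials themselves more narrowly: "Educational materials have been developed and approved by European Medicines Agency (EMA) as additional risk minimization activities for Fabrazyme home infusion therapy".

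Section 8.7 sets the questions and their scoring in Tables 8 and 9.

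- **Receipt (A2).** The HCP version lists the SmPC as code 1, the HCP guide as code 2 and the patient manual as code 3. The patient version lists "Package leaflet for Fabrazyme" as code 1 and the patient manual as code 2. In both surveys only code 2 meets the criterion.
- **Reading (A3, both surveys).** "A3. Have you read the Fabrazyme (agalsidase beta) home infusion educational materials", answered Yes or No, with Yes scored as correct.
- **Use (HCP B1).** "B1. Do you use the educational materials to evaluate and select patients for home infusions", with Yes scored as correct.
- **Use (HCP B4).** A Yes/No question on using the home infusion educational materials when training patients or caregivers, with Yes scored as correct.
- **Use (patient A5).** A frequency question on referring to the educational materials during infusions, with the two most frequent answers scored as correct.

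Section 8.7 defines a positive outcome as more than 70% of participants answering correctly.

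**The concern.** A2 scores receipt of the manual only, so the plan itself treats having the label as not enough. The next questions do not keep that line. A respondent who has just been shown the SmPC or leaflet in a list of materials received is then asked about the materials as a whole. Someone who had and read only the label could give a truthful Yes and be counted as correct.

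The study is meant to evaluate materials developed as additional risk minimisation. If label reading can be credited to the manuals, the error runs one way, towards a finding of effectiveness. B1 and B4 also sit in the Table 8 categories on evaluation for home infusion and on training, which correspond to content areas named in the primary objective in Section 7.

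**Working it through.** **1. The wording, item by item**

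| Item | Names the guide or manual? | Says home infusion materials? | Filter on A2 stated? |
|---|---|---|---|
| HCP A3 | No | Yes | No |
| HCP B1 | No | No | No |
| HCP B4 | No | Yes | No |
| Patient A3 | No | Yes | No |
| Patient A5 | No | No | No |

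HCP B1 and patient A5 are the most exposed, because their stems do not tie the materials to home infusion. The tables do state a filter where one is meant: patient C2 removes the not-applicable answers from its calculation. None of the five items carries a comparable rule.

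**2. The plan's own precision figures**

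The issue depends on no printed figure, but the inputs were checked. With half-width 1.96 × √(p(1−p)/n):

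- n = 34, p = 0.70: 1.96 × √(0.21/34) = 15.4 points, as in Table 6.
- n = 18, p = 0.70: 1.96 × √(0.21/18) = 21.2 points, as in Table 7.

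All other rows of both tables also reproduce to one decimal.

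**3. Counts needed to exceed 70%**

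The tables' criterion of a majority is read here as the >70% rule of Section 8.7.

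- HCPs: 0.70 × 34 = 23.8, so at least 24 of 34 (70.6%).
- Patients/caregivers: 0.70 × 18 = 12.6, so at least 13 of 18 (72.2%).

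**4. A worked example (assumed splits)**

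- HCPs: 20 have and read the guide; 14 have and read only the SmPC. A2 code 2 is 20/34 = 58.8%, not met. If all 14 answer Yes, A3 is 34/34 = 100%, met. Reading of the guide is 58.8%.
- Patients: 10 have and read the manual; 8 have only the leaflet. A2 code 2 is 10/18 = 55.6%, not met. A3 could be 18/18 = 100%, met.

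**5. Sensitivity of one item's result (assumed rates)**

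Take true manual reading as 60%, and let a further share of respondents know only the label and answer Yes. The chance of a positive outcome is the exact binomial probability of at least 24 of 34, or at least 13 of 18, at the observed Yes rate.

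| Label-only Yes | Observed Yes rate | n = 34 | n = 18 |
|---|---|---|---|
| 0 points | 60% | 0.138 | 0.209 |
| 5 points | 65% | 0.313 | 0.355 |
| 10 points | 70% | 0.554 | 0.534 |
| 20 points | 80% | 0.938 | 0.867 |

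On these assumptions, 10 points of label-only Yes answers are enough to turn an unlikely pass into one that is slightly more likely than not.

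**The case against.** The strongest reply is that the term has a natural narrow meaning. Section 6.1 puts the label in the pack; it does not say that the educational materials include it, and it describes those materials as developed for home infusion. Three of the five stems carry the home infusion qualifier and come after A2, where the manuals are listed by title. A reader might infer that the protocol defines the term to include the label, so that every label-only respondent scores as a reader. The text does not support that: such a respondent could score, depending on how the item is understood.

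The full questionnaires are Appendices 1 and 2 and are not shown. Section 8.8.1 promises clear instructions at each question, programmed logic checks and a pilot of the patient survey. A definition or a route from A2 may exist there. This limits the point to the items and scoring as written in Tables 8 and 9.

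In the worked example A2 itself fails, so the report would show that the guide had not reached enough HCPs, and Section 8.7 looks across the key questions rather than at A3 alone. That stands, but A3 would still be reported as met. Cross-tabulating with A2 would find those who never received the manual. It would not find those who received it but read only the label, so analysis cannot fully repair the wording.

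Two further inferences should be set aside. One is that A3 fails as an exposure variable; the protocol plans a descriptive analysis and no comparison of readers with non-readers. The other is that the label reaches users independently of the risk minimisation programme; the protocol does not say so. The knowledge and logbook items do not depend on this wording.

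**Conclusion.** The point holds as a measurement ambiguity in five scored items. As Tables 8 and 9 are written, label-only reading or use could be counted as correct, and any resulting error can only raise the rate compared with the >70% criterion. HCP B1 and patient A5 are the weakest stems.

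It should not be stated as an established upward bias. The documents give no rate of label-only use, so the example (58.8% on A2 against up to 100% on A3) and the pass probabilities show what could happen under assumed rates. The conclusion also assumes that the unseen questionnaires neither define the term nor route respondents by A2. Because the remedy is cheap before fieldwork and only partly recoverable afterwards, the change is worth making.

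**What to change.** 1. Ask A3 separately for each document ticked at A2. Score the HCP guide line in the HCP survey and the patient manual line in the patient survey.
2. Name the document in the other stems: the HCP guide in B1, the HCP guide or the patient manual in B4, and the patient manual in A5. State in each that the SmPC or leaflet alone does not count.
3. Score respondents who ticked no relevant manual at A2 as not having read or used it, keeping them in the denominator. The relevant code is 2, except for HCP B4, where it is 2 or 3. Without that exception, an HCP who trains patients with the patient manual would be wrongly counted as a non-user.

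The cost is five reworded stems, their translation, and one scoring rule set before fieldwork. Reported reading and use rates may be less favourable.

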8.1.1 HCP recruitment

HCPs include both physicians and nurses.

- A) Physicians: A target list of physicians known to be prescribing Fabrazyme home infusion will be provided by the MAH and used for recruitment. Potentially eligible physicians will be approached via telephone or email with information about this study. The method of contacting physicians is dependent on contact details provided in the target list.
- B) Nurses: Based on information provided by the MAH, Nurses play an important role in providing in person medical supervision and education to patients receiving Fabrazyme home infusion in the UK, France, Italy and Finland. Therefore nurses will be included in the HCP sample in these markets. To recruit nurses we will use a mix of both targeted recruitment and via physician referral; for targeted recruitment the MAH will provide a list of external home care provider companies with contact details per market. Potentially eligible nurses will be contacted via telephone or email with information about this study. The method of contacting nurses is dependent on contact details obtained via the physicians or home care providers.

To increase participation in the survey all HCPs on the target lists will be sent a letter of endorsement from the MAH and MAH representative that provides information to validate the regulatory requirement associated with the reason for the survey. Interested HCPs will be asked screening questions to check eligibility for the survey.

Inclusion/exclusion criteria:

- Involved in the treatment of at least 1 patient with Fabry disease in the last 12 months
- Have prescribed Fabrazyme for home infusion and/or monitor, oversee the management, and/or provide in person medical supervision of patients on Fabrazyme home infusion in the last 12 months
- Not a current or ex-employee of Sanofi

If the criteria are met, HCPs are asked to provide consent to participate in the study. Once consent has been provided HCPs is provided with a link to access and complete the main survey.

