8.5 STUDY SIZE

8.5.1 HCP sample size

Given the rarity of Fabry disease and the small prescriber and patient universe for Fabrazyme (agalsidase beta) home infusion as demonstrated in Table 1 in Section '8.2 Setting' we are limited in terms of sample sizes that we can feasibly achieve.

A total sample size of 34 HCPs (physicians and nurses) who prescribe, monitor, oversee the management, and/or provide in person medical supervision of patients on Fabrazyme home infusion will be recruited across key countries previously described in '8.2 Setting'. A minimum of 25 physicians will contribute to the overall HCP sample.

The sample size calculation is based on several factors/assumptions:

- Total number of eligible respondents (assumed to be n=83 based on Table 1)
- Assumption that the target list is high quality and contains up to date contact information and that all respondents have given consent to be contacted by a 3rd party (due to GDPR regulations coming in place in May 2018)
- Assumption of a response rate of 30-40% based on previous experience in recruiting via target list in similar therapy area
 - Example 1 – French study in Gaucher disease – 30-40 respondents were contacted to achieve 15 completes (38-50% response rate)
 - Example 2 – Italian study in Gaucher disease – 65 eligible respondents were contacted to achieve 13 completes (20% response rate)

Given ~83 prescribing physicians across the 5 markets for consideration and a response rate of 30-40%, the maximum physicians expected to take part is therefore 25-34. This sample size reflects ~40% of prescribers across the 5 markets where Fabrazyme (agalsidase beta) home infusion is most prevalent.

In addition to the physicians, the HCP survey will include nurses who are involved in providing in person medical supervision of patients on Fabrazyme home infusion. There are not robust estimates of the numbers of nurses available for recruitment in each country, but we anticipate being able to recruit nurses through the methods outlined in section 8.1.1 in the UK, Italy, France and Finland, based on country-based direction. All markets will be investigated and final inclusion will be confirmed once successful contacts and acceptance to participate has been achieved.

[Table 6](#) denotes the level of precision for a sample of 34 for a selection of response levels to a particular question

Table 6 - Precision estimates for the target HCP sample size (n=34) for 60, 70, and 80% correct response levels

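### Item B1 (use of the materials to select patients) is judged on physicians and nurses together, so nurses who do not select patients can pull it below the 70% mark

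*Protocol*

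**What the plan says.** - **Who is surveyed.** Section 8.1.1 states that "HCPs include both physicians and nurses". Its criteria are joined by and/or, so in-person supervision alone is enough to qualify. On the nurses' part it says: "Nurses play an important role in providing in person medical supervision and education to patients receiving Fabrazyme home infusion".
- **How many.** Section 8.5.1 targets 34 HCPs in total and adds: "A minimum of 25 physicians will contribute to the overall HCP sample". At a total of 34, that leaves room for 0 to 9 nurses.
- **Who evaluates.** Section 6.1 says the decision to move to home infusion "should be made after evaluation and recommendation by the treating physician".
- **The item.** B1 in Table 8 asks: "Do you use the educational materials to evaluate and select patients for home infusions". The only codes are Yes and No. Its criterion is "Majority of HCPs selecting Code 1".
- **The pass mark.** The text of Section 8.7 reads "a positive outcome is defined as at >70% of the survey participants providing a" correct response.
- **A contrast.** For patient item C2, Table 9 provides a not-applicable code and removes those answers from the calculation. B1 has no such code or rule.

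**The concern.** B1 asks about a task that the protocol gives to the treating physician, but its denominator is every HCP. A nurse who supervises infusions and takes no part in selection has only No as a truthful answer. That No describes the nurse's job and says nothing about the materials, yet it counts as a failure of the materials.

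The B1 percentage therefore mixes two things: how far those who select patients use the materials, and how many respondents do not select patients. Section 8.5.1 says that there are no robust estimates of nurse numbers, so the second part is uncontrolled. B1 is one of two items under evaluation of home infusion, the first content area listed in the primary objective. A negative B1 could not be attributed to the materials or to the recruitment mix without a further breakdown.

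**Working it through.** **Inputs from the protocol.** Total of 34 HCPs, at least 25 physicians, pass mark above 70% of participants. **Assumed, because the protocol gives no figure:** Yes rate among physicians *p* = 80% or 90%; Yes rate among nurses *q* = 0%, 25%, 50% or 80%.

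**Plan's own figure first.** Table 6 gives ±15.4 points at 70% for n = 34. The Wald half-width 1.96 × √(0.70 × 0.30 / 34) = 15.4 points, so the table is reproduced and rests on the pooled 34.

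**Pass mark in counts.** 23/34 = 67.6% fails and 24/34 = 70.6% passes, so 24 Yes answers are needed. In 25 physicians alone, 17/25 = 68% fails and 18/25 = 72% passes.

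**Ceiling.** If 9 nurses all answer No, the best possible result is 25/34 = 73.5%, and 24 of 25 physicians (96%) must say Yes.

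**Pooled result with 25 physicians and 9 nurses.** Expected rate = (25*p* + 9*q*)/34. For example, *p* = 0.90 and *q* = 0 gives 22.5/34 = 66.2%. The probability of passing sums over the number of nurses saying Yes, x ~ Bin(9, *q*), the chance that at least 24 − x of 25 physicians say Yes, with physicians ~ Bin(25, *p*).

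| Nurse Yes rate *q* | Expected, *p* = 80% | P(pass) | Expected, *p* = 90% | P(pass) |
|---|---|---|---|---|
| 0% | 58.8% | 0.03 | 66.2% | 0.27 |
| 25% | 65.4% | 0.30 | 72.8% | 0.74 |
| 50% | 72.1% | 0.66 | 79.4% | 0.95 |
| 80% | 80.0% | 0.94 | 87.4% | 0.998 |
| Physicians alone (18 of 25) | 80% | 0.89 | 90% | 0.998 |

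**Dependence on the nurse count** (total 34, all nurses answering No):

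| Nurses | Physicians needed | P(pass), *p* = 80% | P(pass), *p* = 90% |
|---|---|---|---|
| 0 | 24 of 34 | 0.94 | 1.00 |
| 3 | 24 of 31 (77.4%) | 0.73 | 0.99 |
| 6 | 24 of 28 (85.7%) | 0.32 | 0.86 |
| 9 | 24 of 25 (96%) | 0.03 | 0.27 |

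With all nurses answering No, the expected pooled rate drops below 70% once the nurse share exceeds 1 − 0.70/*p*. That is 12.5% at *p* = 80% and 22.2% at *p* = 90%. The protocol allows 9/34 = 26.5%.

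**If the word majority in Table 8 meant more than 50%.** The pass mark would be 18 of 34. With 9 nurses answering No, 18 of 25 physicians would be needed, and the probability of passing is 0.998 at *p* = 90% and 0.89 at *p* = 80%.

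**The case against.** Several objections have force.

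- **Routing.** The HCP questionnaire is Appendix 1, which is not shown. The screener in Table 2 records specialty and personal responsibility to prescribe, and either could keep nurses away from B1. So it cannot be said that nurses are forced to answer No. What stands is that Table 8, as written, states no restricted base.
- **Worst case.** The value 0.27 needs the maximum of 9 nurses, all saying No. If half of them say Yes, the loss at a 90% physician rate is small (0.95), and at a nurse rate of 80% there is none.
- **Pass mark.** Table 8 speaks of a majority. Read as more than half, the effect largely vanishes at a 90% physician rate. The figures here rest on the explicit 70% definition in the text.
- **Direction and weight.** Nurses outside selection can only pull B1 down, so they cannot make ineffective materials look effective. The analysis is descriptive, effectiveness is read across several items, and B2 measures knowledge of the eligibility criteria directly.

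A reader might go further and infer that B2, or the training, infusion-reaction and logbook items (B4 to B6, C1, C2, C4), share the defect and need a 70% verdict per role. The protocol does not support that. B2 is a knowledge question that any HCP can answer, with a don't-know code. Training and supervision lie within the role that Section 8.1.1 gives to nurses, and no comparable mismatch is shown for the logbook items. A separate verdict in 9 nurses would need 7 of 9 (77.8%) and carry a half-width of 1.96 × √(0.21/9) = 29.9 points at 70%.

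**Conclusion.** The point holds for B1 alone. As written, its denominator includes respondents whom the protocol admits for supervision and not for selection, and the verdict can turn on how many of them are recruited. With 9 nurses, the probability of passing ranges from 0.27 to 0.95 at a 90% physician rate, against 0.998 in physicians alone. At an 80% physician rate it ranges from 0.03 to 0.66, against 0.89. These ranges cover nurse Yes rates of 0% to 50%.

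This rests on four assumptions: the total stays at 34; nurses are not routed past B1; the pass mark is more than 70%; and nurses say Yes less often than physicians. The nurse and physician rates are assumed, since the protocol gives none. The low end is a worst case and should not be read as the expected result.

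**What to change.** In Table 8, state that B1 is judged only among HCPs whose role includes evaluating or selecting patients. There are two ways to do this:

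1. Restrict B1 to physicians, using the specialty already collected in the screener. No new data are needed.
2. Add a code for selection not being part of the respondent's role and leave it out of the denominator, as for patient item C2. This keeps any nurse who does take part in selection, but it changes the questionnaire and so must be made before fieldwork.

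If Appendix 1 already routes B1 by role, one line in Table 8 saying so is enough.

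Keep B2 and the training, infusion-reaction and logbook items on all HCPs. A descriptive split by physician and nurse may be shown beside the total, without separate 70% verdicts.

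The cost is precision. With about 25 in the B1 denominator, the half-width at 70% is 1.96 × √(0.21/25) = 18.0 points instead of 15.4.
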